5.3 Screening Failures

Patients who signed the ICF but were found not eligible for the study prior to receiving study drug are defined as screening failures.

For these patients, only limited information will be collected in the electronic case report form (eCRF):

- Informed consent
- Demographics
- Inclusion/exclusion criteria
- SAE and/or death occurring during the screening period

6 Treatment

6.1 Study Drug

The study drug is loncastuximab tesirine, which will be provided as a frozen liquid or a refrigerated lyophilized formulation.

- The liquid formulation will be provided in 10 mL glass vials designed to deliver 3.2 mL of loncastuximab tesirine at a concentration of 5 mg/mL (16 mg loncastuximab tesirine per vial) and stored at -65°C or below. It is a sterile, frozen liquid formulated in 30 mM histidine, 200 mM sorbitol, and 0.02% polysorbate 20, at pH 6.0. Prior to use, the frozen formulation is thawed at ambient temperature, gently swirled to ensure homogeneity, and visually inspected.
- The lyophilized formulation will be provided as a lyophilized white to off-white powder in 8 mL glass vials (10 mg loncastuximab tesirine per vial) and stored at 2-8°C. The lyophilized loncastuximab tesirine is formulated in 20 mM histidine, 175 mM sucrose, and 0.02% polysorbate 20, at pH 6.0. Prior to use, the study drug is reconstituted with 2.2 mL of Sterile Water for Injection to deliver 2.0 mL at a concentration of 5 mg/mL, gently swirled to ensure complete dissolution and homogeneity, and visually inspected. Sterile Water for Injection is to be provided by study sites.

Individual patients will receive the same formulation for their entire treatment.

6.2 Management of Clinical Supplies

Detailed instructions regarding study drug shipment, handling, storage, and preparation are included in the pharmacy manual.

6.2.1 Packaging and Storage

The study drug will be supplied by the Sponsor through the designated packaging, labeling, and distribution center.

Once the package arrives at the study site, the receiving site pharmacy will complete the enclosed procedures to acknowledge receipt.

All study drugs must be stored in a secure area.

- Loncastuximab tesirine liquid formulation: loncastuximab tesirine should be protected from light and stored frozen (-65°C or below). Loncastuximab tesirine should be thawed under ambient conditions.
- Loncastuximab tesirine lyophilized formulation: should be protected from light and stored at 2-8°C.

6.2.2 Preparation and Administration

The study drug solution at the concentration of 5 mg/mL will be the basis for the preparation of the infusion solution. The amount of the product to be diluted will depend on the dose level and the body mass of the patient.

Patients will receive a 30 minutes IV infusion of loncastuximab tesirine on Day 1 of each cycle. Variations in infusion times due to minor differences in IV bag overfill/underfill and the institution's procedure for flushing chemotherapy lines will not result in protocol deviation.

6.2.3 Accountability

The Investigator will maintain accurate records of receipt of all study drugs, including dates of receipt. In addition, accurate records will be kept regarding when and how much study drug is dispensed and used by each patient in the study. Reasons for departure from the expected dispensing regimen must also be recorded. All study drugs will be reconciled and retained or destroyed according to applicable regulations.

6.3 Loncastuximab Tesirine Dosing

Administration of loncastuximab tesirine will be performed by the Investigator or a qualified designee.

Loncastuximab tesirine will be administered as an IV infusion over 30 minutes on Day 1 of each cycle (every 3 weeks) at a dose of 150 µg/kg Q3W for 2 cycles, then 75 µg/kg Q3W. Refer to [Section 6.6](#) for premedication and supportive care.

Patients with a BMI ≥ 35 kg/m² will have their dose calculated based on an adjusted body weight as follows:

$$\text{Adjusted body weight (ABW) in kg} = 35 \text{ kg/m}^2 * (\text{height in meters})^2$$

$$\text{Dose to administer (mg)} = \text{dosage (}\mu\text{g/kg)} * \text{ABW} / 1000$$

Extravasation of loncastuximab tesirine may be associated with local irritation, swelling, pain, or tissue damage. The IV infusion site should be monitored for signs of IV infiltration or drug extravasation, and patients should be instructed to report immediately any signs of IV infiltration or drug extravasation during or after the infusion. Suspected extravasation of loncastuximab tesirine should be managed according to institutional protocol for management of extravasation of cytotoxic chemotherapy. For patients who have a central line, administration of loncastuximab tesirine via this central line should be considered.

6.4 Dose Delays and Modifications

If a patient experiences any Grade ≥ 3 (≥ 2 for edema, effusion, or increased AST/ALT/GGT) non-hematologic toxicity, loncastuximab tesirine must be held until the toxicity resolves to Grade ≤ 1 (Grade 1 or baseline for peripheral neuropathy). In addition, if a patient experiences hematological toxicity of Grade ≥ 3 neutropenia or thrombocytopenia, loncastuximab tesirine must be held until the toxicity resolves to Grade ≤ 2 .

If loncastuximab tesirine dosing is delayed by more than 3 weeks and the toxicity is considered at least possibly related to loncastuximab tesirine, then subsequent doses of loncastuximab tesirine will be reduced by 50%. In addition, the Investigator may reduce the dose of loncastuximab tesirine by 50% for any Grade ≥ 3 (≥ 2 for edema, effusion, or increased

AST/ALT/GGT) toxicity that is possibly related to loncastuximab tesirine, but does not result in dosing delay of more than 3 weeks if they feel it is in the best interest of the patients.

If toxicity requiring dose reduction as described above occurs following the second dose of 150 µg/kg (C2D1), the patient should receive the per protocol-defined dose of 75 µg/kg for Cycle 3.

If toxicity as described above recurs at the reduced dose, subsequent doses of loncastuximab tesirine will be reduced by an additional 50%.

If toxicity as described above recurs after a second dose reduction, study drug must be discontinued permanently.

If loncastuximab tesirine dosing is delayed by more than 5 weeks and the toxicity is considered at least possibly related to loncastuximab tesirine, study drug must be discontinued permanently unless continued administration is approved by the Sponsor.

6.5 Overdose Management

An overdose is any dose of study drug given to a patient that exceeds the dose described in the protocol. There are no data available to determine what the effects of overdose are and whether they can be reversed. Symptomatic treatment and standard supportive care measures for the management of any observed toxicity should be applied.

6.6 Premedication and Supportive care

6.6.1 Premedication

Unless contraindicated, administer dexamethasone 4 mg per os (PO) twice daily (BID) the day before loncastuximab tesirine administration (if possible), the day of loncastuximab tesirine administration (give at least 2 hours prior to administration when not given the day before; otherwise any time prior to administration), and the day after loncastuximab tesirine administration.

Patients who experience an infusion-related hypersensitivity reaction will receive the alternative premedication regimen specified in [Section 6.6.3](#).

6.6.2 Treatment of Edema and Pleural Effusion

Spironolactone at standard doses should be administered for patients with weight gain greater than 1 kg from C1D1, new or worsening edema, and/or new or worsening pleural effusion. The dose of spironolactone may be titrated as clinically indicated. Additional diuretic support may be added if there is further increase in weight, edema, or pleural effusion. Additionally, patients should be advised to monitor their weight on a daily basis, at around the same time (preferably in the morning), and to notify the study site if they gain >1 kg (2.2 pounds) over baseline.

6.6.3 Treatment and Prophylaxis of Infusion-Related Hypersensitivity Reactions

Medications for the treatment of severe hypersensitivity reactions, including anaphylaxis, should be available for immediate use and may be administered according to site standard treatment protocols.

Any patient who experiences an infusion-related hypersensitivity reaction should receive prophylactic treatment in subsequent cycles according to the guidelines below or institutional standard of care:

- On Day 1 of each cycle, patients will be instructed to take dexamethasone 20 mg PO 12 and 6 hours before the start of the loncastuximab tesirine infusion. When necessary, 12 and 6 hours before the first infusion may be defined as “immediately before sleeping” and “immediately after waking up.”
- On Day 1 of each cycle, patients will be given diphenhydramine hydrochloride 50 mg IV 30 minutes before the start of the loncastuximab tesirine infusion.
- On Day 1 of each cycle, patients will be given ranitidine (or equivalent) 50 mg IV 30 minutes before the start of the loncastuximab tesirine infusion.
- For 2 days following administration of loncastuximab tesirine on Day 1, patients are to take dexamethasone 4 mg PO BID.

6.6.4 Skin Rash

Skin rash has been reported in the ADCT-402-101 study, as well as with another investigational agent containing the same PBD warhead (Rudin et al., 2017). The rash has been reported in areas at risk for sun exposure; it is therefore recommended that precautions are taken to avoid prolonged exposure of skin to sunlight.

6.6.5 Other Supportive Care

- Although the study patient population has a low risk for development of tumor lysis syndrome (TLS) compared to patients with acute disease (Cairo et al., 2010), patients should be observed for development of TLS and treated according to site standard treatment protocols.
- As testing in animals showed testicular toxicity (atrophy with reduced spermatogenesis), male patients are advised to consider cryopreservation of sperm prior to treatment with loncastuximab tesirine, where applicable.

6.7 Concomitant Medications and Procedures

All medications (except for the study drug) and procedures will be recorded in the eCRF starting from the ICF signature date or from 14 days prior to C1D1, whichever is earlier, and continuing until at least 30 days after last dose of study drug.

6.7.1 Permitted During Study

All medications or procedures for the clinical care of the patient, including management of AEs, are permitted during the study, except for those listed in [Section 6.7.2](#).

Hematopoietic growth factors are permitted as per American Society of Clinical Oncology guidelines ([Smith et al., 2006](#)).

6.7.2 Prohibited During Study

- Other anticancer therapy with the exception of hormonal therapy for maintenance treatment of breast and prostate cancer.
- Other investigational agents.
- Live vaccines.

7 Discontinuation

The reason for discontinuation and the date of discontinuation will be collected for all patients.

Note: Once discontinued from the study for any reason, patients are not permitted to be re-enrolled.

7.1 Discontinuation from Study Treatment

A patient may be discontinued from the study drug for any of the following reasons:

- Disease progression
- Unacceptable toxicity
- Patient decision
- Major protocol deviation
- The Investigator determines that it is in the best interest of the patient to discontinue study treatment.
- Discontinuation of the study by the Sponsor
- Pregnancy
- Death

IMPORTANT: Study drug discontinuation is not to be automatically considered as withdrawal from the study. Patients discontinuing the study drug will be asked to perform an EOT visit ([Section 4.4](#)) and continue with the Follow-up period ([Section 4.5](#)) as per protocol.

The investigational site should make every effort to complete follow-up per protocol. If patients are unable to return to the site, patient status, including but not limited to survival status, may be obtained by site staff via phone, email, or mail.

7.2 Discontinuation from the Study

A patient may be discontinued from the study for any of the following reasons:

- Withdrawal of consent
- Investigator/Sponsor decision
- Death
- Loss to follow-up

If a patient withdraws informed consent, no additional data will be collected. The Sponsor may continue to use previously collected medical research data prior to the withdrawal consistent with the original authorization.

The study may be terminated at any time, for any reason, by the Sponsor. Patients still receiving study drug should have an EOT visit as described in [Section 4.4](#) and SoE ([Table 1](#)).

7.3 Loss to Follow-Up

Patients who fail to return for protocol follow-up are to be contacted by the investigative site. Following a minimum of two documented unsuccessful telephone calls, the investigative site should send a registered letter to the patient in a final attempt to ensure protocol compliance.

8 Study Assessments and Procedures

Informed consent, as documented by a signed and dated ICF, must be obtained prior to performing any study procedures. Results (e.g., from laboratory tests or radiographic evaluations, etc.) obtained prior to the date of informed consent but within the allowed timeframe for screening may be used for determination of patient eligibility only if obtained as part of standard care.

8.1 Efficacy Assessments

Disease assessments will occur as per schedule of events (SoE) ([Table 1](#)) until progression. Disease assessments should take place at the timepoints specified even if study drug dosing is delayed. Additional disease assessments may be obtained, if clinically indicated.

Imaging and clinical examination for lymphoma will be performed at all disease assessment timepoints. All patients will have positron emission tomography - computed tomography (PET-CT) of the neck/chest/abdomen/pelvis and other areas of known or suspected disease performed at baseline. Patients with PET-avid disease at baseline should have PET-CT for all subsequent disease assessments. If disease is not PET-avid at baseline, computed tomography (CT) or magnetic resonance imaging (MRI) may be used for subsequent disease assessments. Patients whose disease is not PET-avid should have a bone marrow biopsy as part of their baseline staging and disease assessment if clinically appropriate.

Screening (Baseline) imaging must be performed within 4 weeks prior to C1D1.

During the treatment period, imaging will be performed 6 weeks and 12 weeks after C1D1, then every 9 weeks until EOT. Week 6 imaging should be performed within 5 days prior to C3D1 and Week 12 imaging should be performed within 5 days prior to C5D1. All other imaging should be performed within ± 2 weeks of the scheduled time point.

During the follow-up period, patients who discontinued study drug for reasons other than disease progression or initiation of other anti-cancer therapy except stem cell transplant, will have imaging performed every 12 (± 2) weeks until 1 year from EOT, then every 6 months until disease progression, up to 3 years from EOT.

Response data will be collected for patients who receive CAR-T therapy until 90 days after receiving CAR-T therapy.

If a scan has been performed within 8 weeks of EOT, it does not need to be repeated at EOT.

In case of dose delays, disease assessment should be maintained at the frequencies defined above.

The patient's response to treatment will be determined according to the 2014 Lugano Classification Criteria ([Appendix 2](#)) as CR, PR, stable disease (SD), or progressive disease (PD). Images will be obtained according to local site imaging protocols and will be submitted for central review. Submission instructions for central review will be provided in a separate manual.

Central imaging review will be performed using two blinded independent reviewers with adjudication by a third blinded independent reviewer in cases of discordance.

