² Screening imaging (PET-CT) must be performed within 4 weeks prior to C1D1 and the same assessment method should be used throughout the study. Week 6 imaging should be performed within 5 days prior to C3D1 and Week 12 imaging should be performed within 5 days prior to C5D1. All other imaging for disease assessment for patients on study drug should be performed within ± 2 weeks of the scheduled timepoint. Disease assessments should be performed at the timepoints specified even if study drug dosing is delayed. If a scan has been performed within 8 weeks of EOT, it does not need to be repeated at EOT.

³ Disease assessments to be performed in patients having discontinued study drug for reasons other than disease progression.

⁴ ≤3 days prior to administration of study treatment, unless more frequent testing is clinically indicated.

⁵ Not needed if screening assessment was performed within 7 days prior to C1D1.

⁶ Cycle 1 only

⁷ Patients who test positive for ADAs will be requested to supply additional ADA samples as per [Section 8.4.2](#).

Visit Scheduling Windows:

- Treatment Period: visit day ± 2 days (excluding C1D1 which is the reference day)
- EOT: as soon as possible after decision to discontinue the study drug, preferably within 30 days after last dose of study drug, and before initiation of any new anticancer treatment
- Follow-up Period: visit day ± 14 days

1 Introduction and Background

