2.2 Rationale for Dose Selection

For patients with relapsed or refractory non-Hodgkin lymphoma, available data support a loncastuximab tesirine dosing regimen of 150 $\mu\text{g}/\text{kg}$ every 3 weeks (Q3W) \times 2 cycles, followed by a 50% reduction to 75 $\mu\text{g}/\text{kg}$ Q3W for the Phase 2 trial. For safety, particular differences in predicted probabilities (pp) were apparent between the 200 $\mu\text{g}/\text{kg}$ Q3W and 150 $\mu\text{g}/\text{kg}$ Q3W doses, respectively, including Grade ≥ 3 edema (pp=0.2817 vs. 0.1070 in patients with prior stem cell transplant), liver function test-related toxicities (pp=0.4018 vs. 0.1644 in patients with prior relapsed disease; 0.4018 vs. 0.1644 in patients without prior stem cell transplant; pp=0.5208 vs. 0.2203 in patients with body mass index [BMI] of 35 kg/m^2 , and pp=0.4018 vs. 0.1644 in patients with baseline Eastern Cooperative Oncology Group [ECOG] of 0 or 1, respectively), and neutropenia or neutrophil decrease (pp=0.4383 vs. 0.2865).

For efficacy, the decision for initial dosing at the 150 µg/kg dose level is predicated on higher observed and predicted ORR as compared to the 120 µg/kg and lower doses. The decision to dose reduce following 2 cycles of treatment was based on the rapid onset of response observed in a majority of patients (median 2 cycles), and desire to mitigate onset of late-developing and difficult to manage toxicities, such as edema. Initial dosing for 2 cycles is anticipated to optimize the frequency of objective response, while dose reduction in subsequent cycles will permit continued exposure with manageable toxicity to optimize the durability of response.

3 Study Objectives and Endpoints

Table 2. Study Objectives and Endpoints

Objectives	Endpoints
Primary	
Evaluate the efficacy of single agent loncastuximab tesirine in patients with relapsed or refractory DLBCL	ORR according to the 2014 Lugano classification (Cheson et al. 2014) as determined by central review in all treated patients; ORR is defined as the proportion of patients with a best overall response (BOR) of CR or PR
Secondary	

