4.3 Treatment Period

The treatment period starts on the date when a patient receives the first dose of study drug and continues until the date of discontinuation from treatment.

A treatment cycle is defined as 3 weeks (i.e., 21 days). Loncastuximab tesirine will be administered as an intravenous (IV) infusion over 30 minutes on Day 1 of each cycle. Patients will receive 150 $\mu\text{g}/\text{kg}$ Q3W for 2 cycles, then 75 $\mu\text{g}/\text{kg}$ Q3W for subsequent cycles.

Patients may continue treatment for up to one year or until disease progression, unacceptable toxicity, or other discontinuation criteria ([Section 7](#)), whichever occurs first. Additionally, patients benefitting clinically at 1 year may continue treatment after a case by case review with the Sponsor.

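### The 8-week EOT scan waiver can be met by the screening scan, so a patient who stops before Week 6 may have no post-baseline scan until about Week 13 or later, or none at all

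*Protocol*

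**What the plan says.** - **Waiver.** Protocol 8.1 and Table 1 footnote 2 use the same sentence: "If a scan has been performed within 8 weeks of EOT, it does not need to be repeated at EOT". Any scan counts.
- **Screening scan.** Protocol 8.1: "Screening (Baseline) imaging must be performed within 4 weeks prior to C1D1".
- **On-treatment scans.** Protocol 8.1: "During the treatment period, imaging will be performed 6 weeks and 12 weeks after C1D1, then every 9 weeks until EOT". Week 6 imaging is placed in the 5 days before C3D1. Under Protocol 4.3 the treatment period "continues until the date of discontinuation from treatment".
- **Follow-up scans.** Patients who stopped for reasons other than progression or new anticancer therapy (transplant excepted) "will have imaging performed every 12 (± 2) weeks until 1 year from EOT", then every 6 months.
- **Keeping to the timetable.** The rule that scans stay on schedule refers to delayed dosing. Nothing similar covers stopped dosing. Extra scans are allowed when clinically indicated, but are not required.
- **Analysis.** SAP 4.9.1 counts missing response as failure. SAP 4.9.6 censors PFS on Day 1 when there is no post-baseline assessment. SAP 4.9.2, 4.9.5 and 4.9.6 censor events that follow new therapy at the last valid assessment.

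**The concern.** The EOT visit is meant to happen before any new anticancer treatment (Protocol 4.4), so its scan is the natural place to capture the outcome of a patient who stops before Week 6. The waiver allows that scan to be skipped on the strength of a baseline image, which says nothing about response. No other rule then brings the patient back for imaging soon.

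The worst-placed patients are those who stop in order to start another anticancer therapy other than transplant. They are outside scheduled follow-up imaging, so for them the EOT scan is the only planned post-baseline scan.

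Two things are at stake. A patient never scanned is a non-responder by rule and, if alive, adds no follow-up time to PFS. Such patients are unlikely to be a random subset, since they stopped for toxicity, by their own choice or for another treatment. Separately, in patients who stop later without progression, the same waiver followed by a clock that restarts at EOT lengthens the gap between scans just when treatment ends.

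**Working it through.** **1. The plan's own figure.** Protocol 9.1 gives >99% power for N = 140, ORR 20% against 40%, one-sided 0.025. By exact binomial, the smallest r with P(X ≥ r | 0.20) ≤ 0.025 is 39, with actual level 0.0158 and power 0.9990. With the rule of at least 10 responders in 52, these become 0.0155 and 0.9986. The stated figure is reproduced. It serves here only to size the ORR effect.

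**2. When the screening scan meets the waiver.** Let d be the EOT day counted from C1D1 and s the number of days from the screening scan to C1D1 (s ≤ 28). The waiver needs d + s ≤ 56.
- d = 28: s ≤ 28, so every permitted screening scan qualifies.
- d = 42: s ≤ 14.

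**3. First scheduled scan if the Week 6 scan was not done.** First follow-up scan = EOT + 12 weeks (±2).

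| EOT (week) | Screening scan needed | First scan, nominal (window) |
|---|---|---|
| 1 | any permitted | Week 13 (11–15) |
| 2 | any permitted | Week 14 (12–16) |
| 3 | any permitted | Week 15 (13–17) |
| 4 | any permitted | Week 16 (14–18) |
| 5 | ≤ 21 days before C1D1 | Week 17 (15–19) |
| 6 | ≤ 14 days before C1D1 | Week 18 (16–20) |

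For patients who stop to start other therapy (except transplant), no such scan is scheduled.

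**4. Ceiling on the ORR effect.** The documents do not say how many patients stop before Week 6 without progression. Protocol 1.3 gives only 11.1% stopping for TEAEs at any time in Phase 1. Assume 4 to 8 of 140, with 20 to 40% of them responders and every one missed:
- low: 4 × 0.20 = 0.8 responders; 0.8 / 140 = 0.6 points
- high: 8 × 0.40 = 3.2 responders; 3.2 / 140 = 2.3 points

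Effect on power, if a share f of patients is never scanned and true ORR is 40% (rejection at 39 or more of 140): f = 5% (7 patients) gives an effective ORR of 38% and power 99.5%; f = 10% gives 36% and 98.3%.

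**5. Later stoppers.** Take scans at Weeks 6, 12, 21 and 30, and assume EOT is uniform over Weeks 7 to 30 (23 weeks), ignoring windows. The gap around EOT is the time since the last scan plus 12 weeks, or 12 weeks when an EOT scan is done.
- EOT in Weeks 7–12: always waived. Time since last scan runs from 1 to 6 weeks, mean 3.5, over 5 weeks.
- EOT in Weeks 12–21 and 21–30: waived for 8 of 9 weeks each. Time since last scan has mean 4 over each set of 8 weeks.
- Share waived: (5 + 8 + 8) / 23 = 91%.
- Mean gap: 12 + (5 × 3.5 + 8 × 4 + 8 × 4) / 23 = 12 + 81.5 / 23 = 15.5 weeks, which is 1.7 times the 9-week interval.
- Maximum gap: 8 + 12 = 20 weeks, or 22 with the +2-week window.
- More than double 9 weeks (over 18) requires the last scan to be more than 6 and at most 8 weeks before EOT: Weeks 18–20 and 27–29, so 4 / 23 = 17% of EOT times.

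**The case against.** **Sites may not read it this way.** The word *repeated* could be taken to assume an earlier on-treatment scan. The text does not say so, and different sites could read it differently. Likewise, no sentence says outright that the first follow-up scan is due 12 weeks after EOT. It is the natural reading of 8.1 and Table 1, but an inference. Both remarks lower certainty about what would happen in practice; neither closes the gap in the wording.

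**There are partial safeguards.** Extra scans are allowed when clinically indicated, and the SAP may count clinical progression at EOT without imaging as an event in sensitivity analyses of DOR, RFS and PFS. These limit the damage, but they are optional and do not supply a response assessment.

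**The ORR effect is small and runs against the drug.** This stands. A responder who starts no new therapy is scanned in follow-up, and a response seen then still counts. The 0.6 to 2.3 points are therefore a ceiling, reached only if every early-stopping responder starts new therapy or loses the response first. The Phase 1 rate is also a weak anchor: it covers a different population and discontinuation at any time.

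**The longer gap in later stoppers is mostly a design choice.** Largely right. The 12-week follow-up interval is deliberate, and against it the restart at EOT adds about 3.5 weeks on average (15.5 against 12). A gap length is not an estimate of bias.

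**Conclusion.** The gap in the wording is real. For EOT up to day 28 the screening scan always satisfies the waiver, and no scan is then scheduled until nominally Week 13 to 16 (±2), or later for later EOT. Patients who leave for other anticancer therapy may have no post-baseline scan at all. The consequences are avoidable ORR failures and, for patients never scanned and alive, PFS censoring on Day 1. The point is worth fixing because the data cannot be recovered afterwards, although the number of patients affected is unknown and probably small.

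Four stronger conclusions might be inferred, and the documents do not support them:
- *The first scan always falls at Week 16 or later.* EOT at Weeks 1 to 3 gives Weeks 13 to 15, and the window runs in both directions.
- *The primary ORR result is at risk.* The bias is conservative, at most about 0.6 to 2.3 points under the stated assumptions, and power stays at 99.5% even with 5% of patients never scanned.
- *The scan interval more than doubles for anyone who stops.* That happens for about 17% of EOT times in Weeks 7 to 30, under the uniform assumption. The average increase is 1.7-fold.
- *DOR and PFS are shown to be biased upward.* Later detection is possible, but the documents do not give the number of responders who stop without progression, and no bias can be computed from them.

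**What to change.** In Protocol 8.1 and Table 1 footnote 2, state that only a post-baseline scan can satisfy the 8-week waiver. Patients who stop before the Week 6 scan without documented progression would then have the already scheduled disease assessment at EOT (or at Week 6), before any new anticancer therapy. The cost is amendment wording, plus a planned scan actually being done in a handful of patients.

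Optional refinement: when the EOT scan is waived, count the first 12 (±2)-week follow-up scan from the last scan rather than from EOT. For later stoppers this brings the nominal gap back to the 12 weeks the protocol already intends. Existing follow-up scans move earlier, with at most one more per patient. This is secondary and should not hold up the main change.
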